### 8.2 Subgroup analyses

No sub-group analyses are planned.

## 8.3 Frequency of analyses

The primary analysis will take place when follow-up is complete for all recruited participants, any queries on the database has been resolved and the database has been locked. No formal interim analysis is planned.

## 8.4 Economic analysis

The economic analysis aims to estimate the cost effectiveness of commonly used mesh types (e.g. biologic, synthetic) versus no prophylactic mesh in preventing PSH and improving health related quality of life. The intervention groups to be compared will be finalised after recruitment so that they consist of clinically and economically similar interventions in common clinical use. A detailed health economics analysis plan will be prepared prior to locking the database [44].

The primary economic evaluation will be a cost-utility analysis from the NHS perspectives. A secondary analysis will be from a broader perspective (social care, personal costs). We will conduct the primary evaluation at 2 years after index surgery. We estimate that 30% to 40% of participants will have developed a PSH, allowing major differences in the post-surgical cost between the options for different types of mesh to be detected. If differences in the incidence of PSH, quality of life or stoma care costs over 2-years indicate that interpretations of cost-effectiveness might be sensitive to the duration of follow up (e.g. expensive interventions might become cost-effective in the longer term) we will also carry out an evaluation over a lifetime horizon making assumptions about the trajectory of PSH incidence, PSH repair, on-going stoma care costs, QALYs and survival.

NHS costs include those associated with (i) the operation (ii) the post-operative in-patient stay and (iii) stoma care and PSH repair during follow-up. As the insertion of mesh accounts for only a small fraction (5-10 minutes) of the whole procedure, the predominant differential cost of using mesh during the index procedure is the cost of the implant itself. We will estimate the unit cost of mesh based on the purchase price at a range of hospitals participating in the study. We will use NHS reference costs (including excess bed day costs) to estimate the cost of the index hospitalisation, based on length of stay. Subsequent stoma care contacts and products, and stoma-related primary and social care use will be costed using nationally published sources. Information on subsequent in-patient (e.g. PSH repair) and out-patient hospital care from HES will costed using NHS reference costs [45-47].

The main outcome measure for the economic evaluation will be quality adjusted life years (QALYs) estimated using the EuroQol EQ-5D 5L [38] which will be administered at baseline, 6 weeks post-surgery and subsequently at 6 monthly intervals by post or online. We will

estimate the cumulative cost, QALY and net monetary benefit for each patient. Net monetary benefit regression will estimate the association between cost-effectiveness and mesh type, adjusting for a range of potential confounders (i.e. patient characteristics, open/laparoscopic surgery). Uncertainty will be addressed in sensitivity analyses and by using bootstrapping to estimate a cost-effectiveness acceptability curve. Costs and benefits beyond the first 12 months will be discounted in line with recommendations [48].

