## 2.3 Factors influencing PSH development

It is presumed that both surgical factors and patient characteristics can influence the risk of developing PSH. Patient characteristics such as diabetes, obesity and smoking have been linked with compromised tissue healing and, therefore, place patients at a greater risk of PSH. Such factors are also extremely challenging to modify. Surgical factors also have the potential to influence the development of PSH and are more amenable to modification. Such factors may include: the surgical approach (open or laparoscopic); the size, shape and site of the trephine incision in the abdominal wall; route of placement of the bowel

(extraperitoneal or transperitoneal); the use or not of prophylactic mesh at the stoma site and, if mesh is used, how it is used [15].

Of the technical surgical elements elicited above, the use of prophylactic mesh is one of the more widely studied, being the subject of 12 systematic reviews [16-26] and value analyses [27]. The systematic reviews reported that mesh use (compared with no mesh) during initial stoma formation was associated with a lower incidence of PSH. However, it is important to note that the early reviews [24-26] included the same single centre RCTs [28-30], which had methodological limitations. Specifically, these RCTs were small, had limited generalisability, were poorly designed, used different meshes with variable stomata types, varied in follow-up duration and were all at high risk of bias. Subsequent reviews have included more RCTs and concluded similarly that prophylactic mesh results in lower incidence of PSH. However, even the newer RCTs have significant methodological limitations [31] and the findings of these reviews should be interpreted with caution. Better quality multicentre RCTs with longer follow up are ongoing in Europe (PREVENT, STOMA MESH, STOMA CONST).

The costs of mesh vary according to type (e.g. biological mesh for one operation costs about £1000, synthetic mesh less than £20) but, if the more expensive option reduces the risk of PSH or the risk of complications, the post-operative costs should be reduced and a better patient outcome secured. Therefore, it is important to establish the balance of costs and benefits between options for key surgical steps.

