#### 3. Aims and objectives

The CIPHER study (Phase B; CIPHER-B) aims to establish the incidence of symptomatic and radiologically confirmed PSH during a minimum of 2 years follow up. Additionally, CIPHER aims to evaluate the effects of key technical surgical steps during index stoma formation on the risk of subsequent PSH formation.

Specific objectives of CIPHER-B are:

- 1. To describe the incidence of PSH formation within 2 years of formation of all types of stomata other than loop ileostomies;
- 2. To describe the risk of PSH for different types of stoma (end colostomy versus loop colostomy versus end ileostomy)
- 3. To describe the risk of PSH according to how the stoma trephine is created in the anterior fascia of the abdominal wall with respect to location (within or without the rectus sheath) and shape (cross versus circle versus slit);
- 4. To describe the relative risk of PSH following index stoma creation with or without mesh (no prophylactic mesh versus biologic mesh versus synthetic mesh);
- To describe the relative risk of PSH following index stoma creation with prophylactic mesh according to mesh position (intra-abdominal versus sublay/retrorectus versus. onlay);
- 6. To describe the relative risk of PSH with different trephine shapes in the mesh (circle versus cross versus slit versus none (Sugarbaker)).
- 7. To estimate the cost effectiveness of commonly used types of mesh (e.g. biologic, synthetic) versus no prophylactic mesh in prevention PSH and improving health related quality of life.

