#### Figure 2: Data Collection Diagram

#### Footnotes:

- 1. SCNs will record the number of visits at 6 weeks, 6 months and 6 monthly thereafter; we also intend to obtain these data from the database used locally.
- 2. We intend to obtain data for all visits from the database used locally.
- 3. HES and ONS data should record all hospital activity but will only be extracted periodically.

	Time / frequency of data collection with respect to date of index surgery						
	Before	During	Up to discharge	6-weeks after	6-month after	12-month after	6-monthly to study end
Screening log	~						
Consent form	~						
Participant baseline details	~						
Surgical details		~					
Complications			~				
Index hospitalisation resource use		~	~				
SCN contacts with participants and hospital admissions				~	~	~	~
Exercise, support garment data				~	~	~	
EQ-5D-5L; SF-12	~			~	~	~	~
Wound questionnaire			~	~			
Community-based health care					~	~	~
Stoma questionnaire					~	~	~
Questionnaire about living with a stoma						~	
Request CT scans, taken as part of patient's usual care				~	~	~	~
Stoma care products issued				~	~	~	~
In-patient hospital episodes *					~	~	~
Out-patient hospital episodes *					~	~	~

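### Section 8.4 treats the implant as the main extra index cost for every mesh type; at the protocol's prices this is safe for biologic mesh, but for synthetic mesh only if theatre time costs less than about £2–4 per minute

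*Protocol*

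**What the plan says.** Objective 7 (Protocol section 3) is "To estimate the cost effectiveness of commonly used types of mesh (e.g. biologic, synthetic) versus no prophylactic mesh", so synthetic mesh against no mesh is a comparison in its own right.

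Section 8.4 defines the cost scope: "NHS costs include those associated with (i) the operation (ii) the post-operative in-patient stay", followed by stoma care and hernia repair during follow-up. For the operation it gives a reason, "As the insertion of mesh accounts for only a small fraction (5-10 minutes) of the whole procedure", and concludes that "the predominant differential cost of using mesh during the index procedure is the cost of the implant itself". The conclusion is not separated by mesh type.

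Two costing routes for the index admission follow. For the implant: "We will estimate the unit cost of mesh based on the purchase price at a range of hospitals participating in the study". For the admission, NHS reference costs are used "to estimate the cost of the index hospitalisation, based on length of stay". Neither names theatre minutes.

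Prices appear only in the background, section 2.3: "biological mesh for one operation costs about £1000, synthetic mesh less than £20". The timing table in section 5.4 has a row "Index hospitalisation resource use", marked for the period during surgery and up to discharge, without itemising it. Section 8.4 leaves detail to a health economics analysis plan to be prepared before database lock.

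**The concern.** The premise in section 8.4 compares 5–10 minutes with the length of the operation. That shows the time is short. It does not show that the time is cheap relative to the implant, which is what the conclusion needs. With implant prices that differ about fifty-fold between mesh types (£1000/£20 = 50), one rule for both cannot be taken for granted.

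The protocol itself treats theatre time as a cost distinct from the implant: section 2.2.2 lists the two separately when it describes what makes hernia repair expensive.

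At stake is the direction of a small bias. Insertion time is incurred only by patients who receive mesh. If it is not costed, the incremental cost of mesh against no mesh is too low, never too high. The error passes into each patient's cumulative cost and net monetary benefit, and so into the regression that answers objective 7. For synthetic mesh the uncosted part could exceed the part that is counted.

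**Working it through.** The plan states no figure of its own to reproduce, so the check is a break-even calculation.

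**Inputs from the protocol**
- Synthetic implant price P: under £20 (section 2.3); £20 is used as the upper bound.
- Biologic implant price P: about £1000 (section 2.3).
- Insertion time m: 5–10 minutes (section 8.4).
- Yearly appliance cost: £780–1800 for a stoma that is managed effectively, rising to as much as £6000 with a parastomal hernia (PSH) (section 2.2.2).

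**Input not in the protocol**
- Theatre cost per minute c: assumed, £5–20 as the main range.

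**Step 1. Break-even, using document figures only.** Time cost equals implant price when c = P/m.
- Synthetic: £20/5 = £4 per minute; £20/10 = £2 per minute. Because £20 is an upper bound, the true break-even is lower.
- Biologic: £1000/5 = £200 per minute; £1000/10 = £100 per minute.

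**Step 2. Uncosted time and implant share under assumed c.** Time cost = m × c. Implant share of the index differential = P/(P + m × c). Each pair is for 5 and 10 minutes.

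| c (assumed) | Time cost | Synthetic implant share | Biologic implant share |
|---|---|---|---|
| £1/min | £5, £10 | 80%, 67% | 99.5%, 99% |
| £5/min | £25, £50 | 44%, 29% | 98%, 95% |
| £10/min | £50, £100 | 29%, 17% | 95%, 91% |
| £20/min | £100, £200 | 17%, 9% | 91%, 83% |

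For example, synthetic at £5 and 5 minutes is 20/(20 + 25) = 44%; biologic at £20 and 10 minutes is 1000/(1000 + 200) = 83%. The implant predominates for biologic mesh in every row. For synthetic mesh it does so only in the £1 row.

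**Step 3. Does another stated cost pick up the minutes?** The implant is costed at purchase price and the admission from length of stay. An extra 5–10 minutes in theatre will not change length of stay in days. Section 8.4 attaches no unit cost to theatre time, and Table 1 does not list insertion time. No stated route captures it.

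**Step 4. Scale.** The excess appliance cost with a PSH is up to £6000 − £1800 = £4200, or £6000 − £780 = £5220, per year. The smallest offset is £25/£5220 = 0.5 PSH-years per 100 patients and the largest is £200/£4200 = 4.8. So £25–200 per mesh patient is recovered by preventing about 0.5–4.8 PSH-years per 100 patients. Since £6000 is a figure that costs can reach, a typical saving may be smaller and the required offset larger.

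**The case against.** The strongest reply is that section 8.4 does not lay down an implant-only rule. It calls the implant the main component, not the only one. It places the operation within NHS costs, resource use is collected during surgery, and the economic analysis plan and sensitivity analyses are still to come. The under-£20 price is a background illustration, actual purchase prices will be used, and the mesh groups are settled only after recruitment. It is also a costing judgement whether 5–10 minutes should be valued at full average theatre cost.

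Much of this stands, and it makes the point conditional. It does not remove it. The premise is already written, it is the stated reason for concentrating on the implant, and the later plan would inherit it. No route for the minutes is named.

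Three stronger readings are tempting but are not supported:
- *The protocol's own figures show that the premise fails for synthetic mesh.* They give only a break-even. A theatre cost per minute must be assumed to go further.
- *The incremental cost is understated by 56–91%.* Those percentages (25/45 and 200/220) are shares of implant plus insertion time. Objective 7 rests on cumulative two-year cost and QALYs, against which £25–200 once is modest. Nothing here shows that a cost-effectiveness conclusion would change.
- *Fixation materials are wrongly left out although the data exist.* Table 1 records whether the mesh was secured to the abdominal wall and to the stoma serosa. It lists no device, suture type or quantity, so it does not show that fixation can be priced.

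**Conclusion.** The point holds in conditional form. The reasoning in section 8.4 does not support its conclusion for all mesh types. For biologic mesh the conclusion is nevertheless right for any theatre cost below £100 per minute. For synthetic mesh it is right only below about £2–4 per minute, and above £4 the implant is never the larger component.

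If theatre minutes stay uncosted, and a theatre minute costs £5–20 (an assumption), £25–200 per mesh patient is missing. This would modestly understate the cost of synthetic mesh against no mesh, always in favour of mesh. The relative effect for biologic mesh is small: the missing part is 2–17% of its index differential (25/1025 to 200/1200). The synthetic-versus-biologic contrast is largely unaffected if insertion times are similar.

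This is a cheap improvement to the costing, not a threat to the economic evaluation as a whole.

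**What to change.** In section 8.4, or in the health economics analysis plan that follows from it:

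1. Limit the statement that the implant is the main differential cost to biologic (costly) mesh.
2. For both mesh groups, define the differential index cost as implant purchase price plus insertion time multiplied by a published theatre cost per minute. Use the protocol's 5–10 minutes, with both limits in sensitivity analysis.
3. Leave fixation materials out, unless the case report form records enough detail to price them.

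The cost is a change of wording and one extra unit cost. No new data collection is needed, because the time range is already in the protocol. The downside is that synthetic mesh will look slightly less favourable against no mesh.

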## 9. Study management

The study will be managed by the Bristol Clinical Trials and Evaluation Unit (CTEU) of the University of Bristol. The CTEU Bristol is a UK Clinical Research Collaboration registered Clinical Trials Unit. The CTEU Bristol will prepare all the trial documentation and data collection forms, develop and maintain the study database, issue follow-up questionnaires, check data quality as the study progresses, monitor recruitment and carry out study analyses in collaboration with the clinical investigators.

## 9.1 Day-to-day management

The study will be managed by a Study Executive Group (SEG), who will meet either face-toface or by teleconference, every six weeks or more frequently if required. The SMG will be chaired by the Chief Investigator and will include key members of the named research team (see Chief Investigators & Research Team Contact Details).

#### 9.2 Monitoring of sites

## 9.2.1 Initiation visit

Before the study commences, training session(s) will be organised by CTEU Bristol. These sessions will ensure that personnel involved fully understand the protocol, CRFs and the practical procedures for the study. Initiation visits for the CIPHER study will comprise: face-to-face training, teleconference training or online / remote training.

## 9.2.2 Site monitoring

The responsibility to monitor centres participating in the CIPHER study has been delegated to the CTEU by the study sponsor. Monitoring will be conducted in accordance with the risks identified within the study risk assessment. Monitoring, either onsite or centrally, will be performed as required to ensure adherence to ICH-GCP and data collection procedures described in section 5.4.

## 9.3 Study Steering Committee (SSC)

A Study Steering Committee will be convened, but there will not be a Data Monitoring Committee since the study will not alter participants' care. The SSC is made up of coapplicants on the grant and independent members appointed by the funder. The independent members include surgeons, nurses and patient representatives. The independent members include:

- [name] (Chair), Consultant General and Colorectal Surgeon
- [name], Consultant Gastrointestinal and General Radiologist
- [name], Consultant Colorectal Surgeon
- [name], Assistant Professor in Health Services Research
- [name], Stoma Care Nurse
- [name], Bladder and Bowel Nurse
- [name], Patient Representative
- [name], Patient Representative

Members of the research team will attend the meetings to provide information about the study to the committee.

#### 9.4 Patient & Public Involvement (PPI)

This study was discussed at the Association of Coloproctology of Great Britain and Ireland (ACPGBI) Patient Consultation Exercise on March 26th, 2015. Representatives of national inflammatory bowel disease, colorectal cancer, ileostomy and colostomy patient support groups discussed and prioritized 24 different research topics. The prevention and treatment of PSH were considered to be the second highest non-cancer research priority.

During the conception of this project study representatives met with patients, representatives of patient organisations (Colostomy, Ileostomy & Urostomy Associations) and professionals to garner feedback on the proposed study and to continue to engage with the PSH community. We have had patients involved in the design of the study and we have two patient representatives on the Study Steering Committee.

A PPI group will be set up including patients who have had PSH associated with different types of stoma fashioned in the treatment of both benign and malignant diseases. [name] will facilitate this group who will meet regularly to review and provide feedback on various aspects of the study such as reviewing participant documents, increasing participant recruitment and writing lay summaries. The group will also advise on methods and content of communication with participants and, after the study has ended, on dissemination of its findings to potential future patients.

#### 10. Safety reporting

As this study does not require participants to undergo any additional investigations, it is not possible for clinical adverse events to be attributed to study specific procedures.

#### 11. Ethical considerations

#### **11.1** Review by an NHS Research Ethics Committee

Ethical review of the protocol and supporting documentation, including patient information sheets, consent forms and GP letters will be carried out by a UK Research Ethics Committee (REC). Furthermore, any amendments that constitute a substantial amendment will also be reviewed by the REC as appropriate.

CIPHER is a multiphase study and as such REC approvals will be obtained for each phase (A & B) separately. This protocol relates to Phase B of the study, however for completeness the REC reference for Phase A is 16/EM/0155.

#### 11.2 Risks and anticipated benefits

#### 11.2.1 Potential Risks

There is no additional physical risk to patients who agree to take part in this observational study because there is no deviation from standard care or operative strategy. There is a hypothetical risk that patients who develop PSH may be uncomfortable reporting symptoms of their condition on their follow-up questionnaires. However, we feel that this risk is hypothetical and will be outweighed by the potential benefits of the research to future patients and to society.

During their involvement in the study patients may undergo cross-sectional imaging (CT or MRI) for the purposes of disease surveillance or to identify the presence of PSH. Such scans *may* involve the use of ionising radiation (CT), which are associated with a small risk. However, any such scans will be part of standard care and are not study specific procedures.

#### 11.2.2 Potential benefits:

The CIPHER study has the potential to significantly benefit society by addressing an important area of clinical uncertainty for patients at risk of developing PSH. This research priority was supported by a recent survey of the ACPGBI that ranked optimisation of methods to prevent and repair PSH as the second most important research question not related to cancer [49].

#### 11.3 Informing potential study participants of possible benefits and known risks

Information about possible benefits and risks of participation will be described in the PIL.

#### 11.4 Obtaining informed consent from participants

All participants will be given or sent a Patient Information Leaflet (PIL) and the opportunity to deliberate before being approached for their written informed consent. The majority of patients, those undergoing either elective or expedited (but not urgent or immediate) surgery to form a stoma, will meet with a SCN prior to surgery, who will describe the study

and address any concerns that the patients may have. In some instances, consent may be taken retrospectively following the participant's surgery. When this happens, participants will have the same opportunity to deliberate about participation before being approached for their written informed consent. If the patient declines the study, their intraoperative data will be deleted.

The member of the research team taking consent will be appropriately trained and delegated to perform their role. A copy of the signed Informed Consent form, along with a copy of the PIL will be given to the study participant to keep. Furthermore, the original signed informed consent form will be retained for trial records and a further copy will be placed in the patient's medical notes.

